1. BACKGROUND AND RATIONALE

1.1 Background

In the UK, 4.5% of all people aged over 40 are estimated to live with diagnosed Chronic Obstructive Pulmonary Disease (COPD), based on Read codes recorded in Electronic Medical Records (7). The UK is among the top 20 countries for COPD mortality worldwide (8).

COPD is a heterogeneous condition with patients showing varying clinical and pathophysiological features. The identification of COPD phenotypes with distinct characteristics may allow targeted treatment strategies directed towards specific biological pathways.

Eosinophilic inflammation is thought to be a characteristic feature of asthma rather than COPD. However, studies have shown that there is a subset of COPD patients with eosinophilic airway inflammation, even after exclusion of patients with any features of asthma (1). Interestingly, this subset of patients with COPD exhibit the greatest response to corticosteroid treatment (4, 9) and tailoring of therapy based on sputum eosinophil counts is more effective in reducing exacerbations than treatment according to traditional guidelines (5). This suggests that there is a sub-phenotype of COPD with an eosinophilic type of airway inflammation similar to that observed in patients with asthma (10).

In a study performed in patients with COPD from the general population of Denmark, blood eosinophil levels above $0.34 \times 10^9 / L$ were associated with a 1.76-fold increased risk for severe COPD exacerbations requiring hospitalization and with a 1.15-fold increased risk for exacerbations not requiring hospital admission (11).

Previous work conducted at OPRI confirmed the increased risk of exacerbations with high blood eosinophil counts in real-life UK patients with COPD from the Optimum Patient Care Research Database (OPCRD) when using a higher cut-point of $\geq 0.45 \times 10^9 / L$, observed in 10% of the population (submitted for publication). However, the association was limited to patients who were not actively smoking. Ex-smokers with high blood eosinophil counts showed a 32% higher rate of exacerbations than ex-smokers with normal eosinophil counts. The association was found in patients treated with ICS and in patients in GOLD groups B to D, and was not influenced by any prior recording of asthma.

[figure not shown]

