2.5 Study designs

2.5.1 Objective 1

The index date (ID) of objective 1 will be the most recent date of a recorded blood eosinophil count, measured at the time of stable disease, defined as no COPD exacerbation within 4 weeks prior to or at ID and no change in treatment regimen, ICS dosage and substance during the study period (Figure 1).

[figure not shown]

Figure 2. Study design objective 1

Patient's demographics and clinical characteristics will be described and potential confounders will be assessed in a baseline year prior to ID.

The association between high blood eosinophil counts (at ID) and (moderate or severe) COPD exacerbations in the subsequent year will be assessed in subgroups of patients defined by smoking status (active smoker in baseline year or not) and the following treatments in the baseline year (22):

1. Short-acting bronchodilators as required only (SABA and/or SAMA)
2. Maintenance therapy with LAMA and/or LABA
3. ICS / LABA in combination inhaler
4. Triple therapy: ICS + LABA + LAMA

The primary definition of "high eosinophil counts" will be $\geq 0.45 \times 10^9/L$, based on our previous work. Sensitivity analyses will be performed using 0.25, 0.35 and 0.55 as cut-points.

Sensitivity analyses will be performed in the subgroup of patients with COPD who have never been diagnosed with asthma, i.e., no diagnostic Read code for asthma recorded ever.

Additional analyses will be performed to evaluate whether the Medication Possession Ratio (MPR) for maintenance treatments (ICS / LAMA / LABA) modifies the associations by:

1. Including interaction terms of blood eosinophil counts and MPR into the regression model (continuous or categorical depending on best model fit) to explore whether MPR significantly modifies the association and at which values
2. Repeating analyses in patients with good adherence to ICS, using the widely used cut-point of $MPR \geq 80\%$ for therapy options 3 and 4

2.5.2 Objective 2

The ID of objective 2 will be the date of the most recent first discharge from hospital admission for COPD exacerbation occurring within one year after a blood eosinophil count measured at the time of no recent exacerbation (Figure 3). Patients will be followed after ID until re-admission or death to a maximum of one year after each index date.

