3.3 Other Variables and Covariates

3.3.1 Patient demographics / baseline characterisation

The following baseline characteristics will be described for comparison groups:

1. Age group at index date (years):
2. Sex
3. Smoking status, Read code closest to and within 5 years prior to index date
 - a. Never smoker
 - b. Ex-smoker
 - c. Current smoker
4. BMI, calculated from height and weight data if available⁶ and taken from practice recorded BMI value if not, within 10 years prior to index date
 - a. Underweight: <18.5
 - b. Normal weight: ≥ 18.5 and <25
 - c. Overweight: ≥ 25 and <30
 - d. Obese: ≥ 30
5. Comorbidities (Diagnostic Read code prior to index date):
 - a. Asthma
 - a. Never
 - b. Active⁷
 - c. Ever, not active
 - b. Allergic / non-allergic rhinitis
 - a. Never
 - b. Active
 - c. Ever, not active
 - c. Eczema diagnosis
 - a. Never
 - b. Active
 - c. Ever, not active
 - d. Nasal polyps ever
 - e. Helminth infections
 - f. Chronic sinusitis diagnosis ever
 - g. Gastro-oesophageal reflux disease (GERD)
 - h. Diabetes Mellitus ever
 - i. Osteopenia / Osteoporosis ever
 - j. Hypertension ever
 - k. Obstructive Sleep apnoea ever
 - l. Cataract ever
 - m. Ischaemic heart disease ever
 - n. Heart failure ever

⁶ Weight (kg) divided by height (metres) squared

⁷ For comorbidities, 'active' refers to those for which a diagnosis was recorded within the baseline year and/or a prior diagnosis was accompanied by a prescription for the comorbidity within the baseline year. 'Ever' refers to diagnosis at any time before or during the baseline period

- o. Psychiatric conditions / Anxiety/ Depression ever
 - p. Sleep disorders ever
 - q. Chronic kidney disease ever
 - r. Osteoporosis (Read code diagnosis or osteoporosis drugs [bisphosphonates, denosumab, strontium ranelate or teriparatide] ever
6. Charlson co-morbidity index: based on diagnoses ever
- a. 0
 - b. 1-4
 - c. 5-9
 - d. ≥ 10
7. Most recent FEV₁ % predicted, mean (SD) and categorical
- a. $\geq 80\%$
 - b. 50–79%
 - c. 30-49%
 - d. $< 30\%$
 - e. Unknown
8. Modified Medical Research Council (MRC) dyspnoea score, within 5 years of the index date
- a. 0-1
 - b. ≥ 2
 - c. Unknown
9. GOLD groups, defined based on a combined assessment of symptoms, spirometry and exacerbation risk as follows:
- a. GOLD A: FEV₁ % predicted ≥ 50 and ≤ 1 COPD exacerbation and no hospitalization for COPD in baseline year and mMRC 0–1

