3.4 Statistical Methods – General Aspects

Summary statistics are provided for all baseline and outcome variables, for the complete dataset and by comparison groups. For continuous variables, these include:

- Sample size (n)
- Percentage non-missing
- Mean \pm Standard Deviation for normally distributed variables
- Median and Inter-quartile Range (25th and 75th percentiles) for non-normally distributed variables

For number of events per year, the summary statistics include:

- Sample size (n)
- Count and Percentage by category (distribution): 0, 1, 2, 3 and ≥ 4

For other categorical variables, the summary statistics include:

- Sample size (n)
- Count and Percentage by category (distribution)

Characteristics are compared using the chi-squared test for categorical variables and a Student's t-test for normally distributed continuous variables or a Mann-Whitney test for non-normally distributed continuous variables.

3.4.1 Outcome analyses sub-study 1

Analyses will be performed in patients on different treatment regimens, adjusted for potential confounders (see paragraph 3.3.2) in two populations:

1. The full population of patients with COPD
2. A subpopulation of patients with "classical COPD" who had FEV₁/FVC <0.70 recorded within 5 years prior to the index date, never received an asthma diagnosis and have a smoking history

Negative binomial regression is performed to estimate RRs with 95% CI for the association between high blood eosinophil counts and the number of outcome events in the outcome period.

The primary definition of high blood eosinophil counts will be $\geq 0.45 \times 10^9/L$, based on previous work. Sensitivity analyses will be performed using ≥ 0.25 , $\geq 0.35 \times 10^9/L$ and $\geq 0.55 \times 10^9/L$ as cut-points.

Additional analyses will be performed to evaluate whether the MPR modifies the associations by including interaction terms of blood eosinophil counts and MPR into the regression model

(continuous or categorical depending on best model fit).

Analyses will be repeated in patients with good adherence, defined as $MPR \geq 80\%$.

Sensitivity analyses will be performed for the full population after exclusion of patients with any diagnostic Read code for asthma recorded ever.

Additional analyses will be performed to study whether the associations are different in never-smokers and ex-smokers in the full populations.

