Confounding will be evaluated by comparing the coefficients for the effect of high eosinophil counts on the outcome event in models with and without the variable included. A change in coefficient of $\geq 5\%$ will be considered relevant.

Because there are patients with missing data on BMI and smoking habits, these variables are only kept in the model if there was relevant confounding.

In the case of relevant confounding by BMI or smoking habits, these variables are included as categorical variables with a separate category for patients with missing data. This procedure will be evaluated by comparing the coefficients for the effect estimate obtained from these models with those from a model analysing only patients with complete data available.

For the variable “age at index date” a categorical and a continuous variable (with evaluation of polynomial functions) are evaluated for best model fit and greatest confounding effect.

Final models will be arrived at following a forward-selection procedure, in which variables will be added one-by-one and were retained if the coefficient for the effect estimate (high eosinophil count) changed by $\geq 5\%$. Co-linearity will be checked by evaluating variance inflation factors (VIFs).

Comorbidities, which are univariately associated with blood eosinophil counts are evaluated for potential confounding effects separately as there are uncertainties about the underlying mechanism. These variables could be potential confounders if they are predictive of the occurrence of exacerbations through a mechanism other than the one under study. However, if they are intermediate factors on the causal pathway from high eosinophil counts to event occurrence, adjustment would be inappropriate. As these underlying mechanisms are unknown, effects of $\geq 5\%$ on the effect estimate by adjustment will be separately reported.

3.4.2 Outcome analyses sub-study 2

The crude (unadjusted) risks of re-admission to hospital for COPD are reported in a life-table (Table 1) and Kaplan-Meier curves are constructed for the total population and for patients with and without high blood eosinophil counts for the maximum follow up period of 12 months after hospital discharge. Comparisons are made with a long-rank analysis.

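### Smoking status taken from the single closest code within 5 years can file ex-smokers as never-smokers and dilute the planned never- versus ex-smoker analysis

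*Protocol*

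**What the plan says.** Protocol section 3.3.1, item 3, sets three classes (never, ex, current) from "Smoking status, Read code closest to and within 5 years prior to index date". It is the only place where the protocol defines these three classes.

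The same list treats other lifetime attributes differently. For comorbidities, footnote 7 reads "Ever' refers to diagnosis at any time before or during the baseline period". That footnote is confined to comorbidities.

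Smoking is used in several places:

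- Section 2.5.1 stratifies objective 1 by "smoking status (active smoker in baseline year or not", and section 2.5.3 divides the objective 3 subgroups in the same two-way manner.
- Section 3.4.1 plans additional analyses to "study whether the associations are different in never-smokers and ex-smokers in the full populations".
- Section 3.4.1 also defines a classical COPD subpopulation whose members "never received an asthma diagnosis and have a smoking history". It names neither a source variable nor a look-back for the smoking part.
- On adjustment, section 3.4.1 states "Because there are patients with missing data on BMI and smoking habits, these variables are only kept in the model if there was relevant confounding". If smoking is kept, missing values get their own category, and the result is compared with a complete-data model. Section 3.4.2 carries this procedure over to sub-study 2.

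No section says what happens when a 'never' code follows an earlier smoking code.

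**The concern.** Current smoking changes over time, so the most recent code is a sensible source for it. Having ever smoked does not change: one valid current- or ex-smoker code means the patient is not a never-smoker, whatever is recorded later. A rule that looks at one code cannot establish 'never'.

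The never/ex comparison has a real purpose. Section 1.1 reports from earlier work that "Ex-smokers with high blood eosinophil counts showed a 32% higher rate of exacerbations" than ex-smokers with normal counts. The hypothesis in section 1.3 covers everyone who is not actively smoking. Comparing never- with ex-smokers is the planned check on whether the ex-smoker result carries over to never-smokers. Ex-smokers filed as never-smokers pull the two estimates together, so a real difference could be missed, or the association could seem to extend to never-smokers when it does not.

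Section 3.5.2 accepts that the validity of individual records cannot be assessed. Contradictory codes within one patient are an error that the data themselves can reveal, and this rule discards that information.

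**Working it through.** The protocol states no figure for this point, so there is nothing to reproduce. The check has two parts.

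**1. The rule applied literally.** Take a patient coded as a smoker 8 years before the index date and as 'never' one year before. The closest code inside 5 years is 'never', so the patient is a never-smoker. Take another whose only smoking code, 'smoker', is 6 years old. No code lies inside the window, so the patient has no smoking status.

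**2. Possible size.** Let N be the true never-smoker share, E the true ex-smoker share, and m the share of ex-smokers whose closest code is 'never'.

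- Ex-smokers within the recorded never group: c = mE / (N + mE).
- Rate ratio seen in that group: (1 − c) × RR(never) + c × RR(ex), assuming equal baseline rates and equal prevalence of high eosinophils in both.

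Inputs: RR(ex) = 1.32 from section 1.1. Section 3.6.1 expects one third active smokers, leaving two thirds for never- and ex-smokers together. E = 55%, N = 8 to 12%, m = 2 to 10% and RR(never) = 1.00 are assumptions; the protocol gives none of them.

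- Low end (m = 2%, N = 12%): c = 0.011 / (0.12 + 0.011) = 0.011 / 0.131 = 8.4%. Observed RR = 1 + 0.32 × 0.084 = 1.03. The ratio of the ex-smoker to the never-smoker RR falls from 1.32 to 1.29.
- High end (m = 10%, N = 8%): c = 0.055 / (0.08 + 0.055) = 0.055 / 0.135 = 40.7%. Observed RR = 1 + 0.32 × 0.407 = 1.13. The ratio falls to 1.17.

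Under the same assumptions the observed difference between the two rate ratios is (1 − c) times the true one. The share of the difference that is lost therefore equals c, whatever the true never-smoker value.

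**Wider grid**, with E = 2/3 − N. Each cell gives c and the observed RR in the recorded never group.

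| m | N = 5% | N = 10% | N = 15% |
|---|---|---|---|
| 1% | 11%, 1.04 | 5%, 1.02 | 3%, 1.01 |
| 5% | 38%, 1.12 | 22%, 1.07 | 15%, 1.05 |
| 10% | 55%, 1.18 | 36%, 1.12 | 26%, 1.08 |
| 20% | 71%, 1.23 | 53%, 1.17 | 41%, 1.13 |

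The effect is negligible if conflicting codes are rare and substantial if they are not. It is sensitive to m because the never group is assumed to be small.

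**The case against.** Several points on the other side are sound.

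- *Reach.* The never/ex comparison is an additional analysis in one sub-study. The main strata separate active from not active smokers, and mixing up never and ex does not alter them. In sub-studies 1 and 2 smoking enters the model only if it confounds, and the missing category is checked against complete data. This stands, and it limits the point.
- *Classical COPD.* A reader might infer that the 5-year rule also damages this population by dropping true ever-smokers. The protocol does not support that. It does not tie the smoking-history criterion to the item 3 variable, and the 5-year limit in that definition belongs to FEV1/FVC. Any earlier smoking code could satisfy it. If the variable were reused, the share of true ever-smokers left out would be mE / (E + 1/3): about 0.6% at m = 1%, 3% at m = 5%, and 12 to 13% at m = 20%. What can be said is that the criterion is undefined.
- *Sample size.* A reader might turn the dilution into an inflated sample size from the effect size alone. (ln 1.32 / ln of the diluted ratio)² gives about 1.2 and 3.2 at the two ends of the range. Contamination also enlarges the recorded never group, which lowers the variance, so these figures overstate the loss and I do not rely on them.
- *Analysis plan.* Conflicting codes could be handled in a statistical analysis plan that is not shown. But the protocol does not leave the matter open: it states an operative rule, and that rule is the one at issue.
- *Fallible smoking codes.* Giving precedence to any earlier smoking code assumes that it is right. One erroneous code would make a true never-smoker an ex-smoker. This is a genuine but small cost, and it can be checked.
- *The lone old code.* A single smoker code from 6 years ago proves ever-smoking but cannot separate current from ex. A longer look-back does not settle that patient in the three-level variable.

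**Conclusion.** The point holds for the never/ex distinction. Followed as written, item 3 of section 3.3.1 files some ex-smokers as never-smokers and can dilute the additional comparison in section 3.4.1. With 55% ex-smokers, 8 to 12% true never-smokers and 2 to 10% of ex-smokers last coded 'never', 8 to 41% of the recorded never group would be ex-smokers. A true rate ratio of 1.00 would then show as 1.03 to 1.13. These inputs are assumptions, and at 1% miscoding the shift is only 0.01 to 0.04.

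The protocol does not support the stronger conclusion that the rule undermines the main smoking strata or smoking adjustment throughout the study. The change is worth making because it is cheap and the present rule has no advantage for identifying never-smokers, but no primary analysis depends on it.

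**What to change.** In section 3.3.1 item 3, keep the closest code within 5 years for current versus not current. Class a patient as 'never' only if no current- or ex-smoker code exists at any time up to the index date; where the closest code is 'never' but such a code exists, recode the patient as ex-smoker.

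In section 3.4.1, and in the matching synopsis text, state that a smoking history for classical COPD means any current- or ex-smoker code up to the index date, without the 5-year limit.

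Report how many patients are reclassified, and repeat the never/ex analysis under the closest-code rule. The count supplies the missing conflict rate, and the repeat shows whether isolated erroneous smoking codes matter.

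The cost is two sentences of definition, a longer look-back on codes already in the record, and one extra run of an additional analysis. No new data are needed.

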3.3.2 Potential confounders of association between high eosinophil counts and outcomes

Analyses will be adjusted for the following potential confounders:

1. Age
2. Sex
3. Smoking status

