4. BMI
5. Asthma
 - a. Never
 - b. Active⁸
 - c. Ever, not active
6. Allergic / non-allergic rhinitis:
 - a. Never
 - b. Active
 - c. Ever, not active
7. Eczema diagnosis:
 - a. Never
 - b. Active
 - c. Ever, not active
8. Nasal polyps ever
9. Charlson comorbidity index

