4. BMI
5. Blood eosinophil count
6. Most recent MRC score
7. Most recent FEV₁ % predicted, with separate category for missing
8. Baseline number of exacerbations
9. Comorbidities (Diagnostic Read code prior to index date):
 - a. Asthma ever
 - b. Allergic / non-allergic rhinitis
 - a. Never
 - b. Active⁹
 - c. Ever, not active
 - c. Eczema diagnosis

⁸ For comorbidities, ‘active’ refers to those for which a diagnosis was recorded within the baseline year and/or a prior diagnosis was accompanied by a prescription for the comorbidity within the baseline year. ‘Ever’ refers to diagnosis at any time before or during the baseline period

⁹ For comorbidities, ‘active’ refers to those for which a diagnosis was recorded within the baseline year and/or a prior diagnosis was accompanied by a prescription for the comorbidity within the baseline year. ‘Ever’ refers to diagnosis at any time before or during the baseline period

- a. Never
 - b. Active
 - c. Ever, not active
 - d. Nasal polyps ever
 - e. Chronic sinusitis diagnosis ever
 - f. Gastro-oesophageal reflux disease (GERD) ever
 - g. Diabetes Mellitus ever
 - h. Osteopenia / Osteoporosis ever
 - i. Hypertension ever
 - j. Obstructive Sleep apnoea ever
 - k. Cataract ever
 - l. Ischaemic heart disease ever
 - m. Heart failure ever
 - n. Psychiatric conditions / Anxiety/ Depression ever
 - o. Sleep disorders ever
 - p. Chronic kidney disease ever
 - q. Osteoporosis (Read code diagnosis or osteoporosis drugs [bisphosphonates, denosumab, strontium ranelate or teriparatide] ever
10. Charlson comorbidity index
11. Therapy prescribed in the baseline year (yes/no)
- a. ICS / LABA
 - b. SABA
 - c. SAMA
 - d. LAMA
 - e. Theophylline

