3.5 Bias

3.5.1 Methods to Minimize Bias

Analyses will be adjusted for all potential confounders of the associations by multiple regression analysis.

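### The adjustment list omits baseline-year exacerbations, FEV1 % predicted and mMRC, so residual differences in history and severity within a regimen-and-smoking stratum are neither controlled nor tested

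*Protocol*

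**What the plan says.** Section 3.3.2 opens with "Analyses will be adjusted for the following potential confounders" and lists age, sex, smoking status, BMI, asthma, rhinitis, eczema, nasal polyps and, last, "9. Charlson comorbidity index". Section 3.4.1 points sub-study 1 to this list, and 3.4.2 applies the same procedure to the re-admission hazard ratio of sub-study 2.

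The three missing variables appear elsewhere in the protocol:

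- Section 3.3.1 describes "7. Most recent FEV₁ % predicted, mean (SD) and categorical" and "8. Modified Medical Research Council (MRC) dyspnoea score, within 5 years of the index date", each with a category for unknown values. Item 9 builds the GOLD groups from criteria such as "≤ 1 COPD exacerbation and no hospitalization for COPD in baseline year", so baseline-year exacerbations have to be derived for every patient who is classified.
- Section 3.3.3 makes the MRC score, FEV1 % predicted and "Baseline number of exacerbations" candidate predictors of next-year costs.

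Section 3.4.1 builds the final model by forward selection and keeps a variable if it moves the eosinophil coefficient by at least 5%. Comorbidities that might lie on the causal pathway are assessed apart, and their effect is reported separately. Section 3.5.1 then states: "Analyses will be adjusted for all potential confounders of the associations by multiple regression analysis".

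**The concern.** Exacerbation history and lung function are obvious candidates for predicting next year's exacerbations, and the protocol itself treats them as candidate predictors of next-year costs. If patients with high counts already exacerbated more in the baseline year, or had worse lung function, some of the rate ratio reflects that difference. If the imbalance runs the other way, an effect may be partly hidden. The 5% rule is the plan's safeguard against confounding, but it is offered only the listed variables and certain comorbidities, so it cannot flag these three. The bias statement in 3.5.1 therefore promises more than the plan delivers. Readers of the sub-study 1 results could also take the association to hold over and above exacerbation history and severity when no model has examined that.

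**Working it through.** **1. Set the sections side by side.**

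| Variable | Derived at baseline (3.3.1) | Cost model (3.3.3) | Confounder list (3.3.2) |
|---|---|---|---|
| Baseline-year exacerbations | needed for item 9 | item 8 | absent |
| FEV1 % predicted | item 7 | item 7 | absent |
| mMRC / MRC | item 8 | item 6 | absent |

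No other section adds them to the models of sub-studies 1 or 2. The pathway argument in 3.4.1 concerns comorbidities only and gives no reason for leaving these three out.

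**2. The plan's own figure.** For a rate ratio of 1.3, a control rate of 0.68, 10% high counts and 80% power, section 3.6.1 states 1,645 patients per therapy group. A two-sided Poisson comparison on the square-root scale gives (1.960 + 0.842)² × (1/0.1 + 1/0.9) / [4 × (√0.884 − √0.68)²] ≈ 1,632, within 1% of that. The figure is not in dispute, and this point does not rest on power.

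**3. Possible size of the bias (illustration).** Section 3.6.3 expects 25% of triple-therapy patients to have frequent or hospitalised exacerbations. I take this as the share in the normal-count group. Two quantities are assumed because the protocol gives neither: the share f in the high-count group, and the ratio R of outcome rates between high-risk and other patients. With no eosinophil effect, the apparent rate ratio is

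[1 + f(R − 1)] / [1 + 0.25(R − 1)]

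| f | R = 2 | R = 3 | R = 4 |
|---|---|---|---|
| 20% | 0.96 | 0.93 | 0.91 |
| 30% | 1.04 | 1.07 | 1.09 |
| 35% | 1.08 | 1.13 | 1.17 |

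At R = 3 these are 1.4/1.5, 1.6/1.5 and 1.7/1.5. To produce the whole of 1.3, f would have to reach 62.5%, 47.5% or 42.5% at R = 2, 3 or 4. An imbalance of the size tabulated therefore shifts the estimate without explaining all of it.

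**4. Against the plan's own threshold.** At a rate ratio of 1.3 the coefficient is ln 1.3 = 0.262. Five per cent of it is 0.0131, a factor of exp(0.0131) = 1.013. Solving the formula for f:

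- R = 2: (1.25 × 1.013 − 1)/1 ≈ 26.6%
- R = 3: (1.5 × 1.013 − 1)/2 ≈ 26.0%
- R = 4: (1.75 × 1.013 − 1)/3 ≈ 25.8%

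An imbalance of one to two percentage points would thus count as relevant under 3.4.1, if the variable were tested.

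**5. What adjustment does if the effect is persistent.** Assume gamma-distributed individual rates with dispersion k and an eosinophil effect of 1.3 in both years. At a given baseline count, the expected next-year rate is proportional to μ/(1 + kμ). With k = 1, the adjusted ratio is (0.884/1.884)/(0.68/1.68) = 0.469/0.405 = 1.16. The adjusted figure then answers a different question from the unadjusted 1.30.

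**The case against.** The strongest reply is that sub-study 1 asks only about an association within treatment and smoking subgroups, and hypothesis 1.3 speaks of a marker of a phenotype. The protocol refers to an independent effect of the count only for the cost model, which does include these variables. For a lasting phenotype, earlier exacerbations and lost lung function may be consequences of the eosinophilia, so leaving them out of the main model is defensible. This stands, and step 5 shows why. It justifies keeping the planned model. It does not justify leaving the omission unexplained or unexamined, because 3.4.1 already has a way of handling variables of uncertain causal role: report the effect of adjusting for them.

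Stratification also counts. Four regimens, smoking status, unchanged therapy over both years and the exclusion of chronic oral corticosteroid users all narrow severity differences. A reader might infer that the rate ratio cannot be separated from history and severity at all; the design does not support that. Separation is partial. The 25% high-risk share within triple therapy alone shows how much variation in risk remains inside one regimen.

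Two practical objections also hold:

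- mMRC is taken "Modified Medical Research Council (MRC) dyspnoea score, within 5 years of the index date", which does not restrict it to earlier values, and the extent of missing FEV1 and mMRC is not given.
- In sub-study 2 the index date is hospital discharge and the count may be up to a year older. Baseline-year COPD admissions can therefore fall after the count, or include the index admission itself. Simply adding them would condition on events after the exposure.

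**Conclusion.** The omission is real, and it contradicts 3.5.1. Residual differences in exacerbation history and severity within a stratum are uncontrolled and escape the 5% rule. The gap carries over to sub-study 2. The documents give neither the size nor the direction of any bias. The range of 0.93 to 1.13 assumes R = 3 and high-count shares of 20% to 35% against 25%, and it is an illustration only.

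A reader might also infer that the model with these variables would settle whether the count predicts independently. It would not. The formula in step 5 applies equally to an unmeasured difference in proneness to exacerbate. With k = 1, a crude ratio of 1.17 that is due wholly to such a difference becomes (0.7956/1.7956)/(0.68/1.68) = 0.443/0.405, about 1.09, after adjustment. One year's count is an imperfect measure of that proneness. The two estimates are informative together, and neither is decisive alone.

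**What to change.** 1. **Sub-study 1:** keep the planned model. Add a second model per stratum with baseline-year exacerbations (0, 1, 2, 3, ≥4, the categories already set in 3.4), FEV1 % predicted and mMRC. Use only values recorded on or before the index date, with the existing categories for unknown values. Apply the complete-case comparison that 3.4.1 sets for BMI and smoking.
2. **Reporting:** give both rate ratios side by side, as 3.4.1 does for comorbidities of uncertain role. Do not describe the association as independent of exacerbation history or severity on the first model alone.
3. **Section 3.5.1:** replace the claim of complete adjustment with a statement of which variables each model includes.
4. **Sub-study 2:** make the same with-and-without comparison using only severity and exacerbation variables measured before the eosinophil count, and exclude the index admission. The look-back window must be stated, because section 2.3 guarantees continuous data only for the year before discharge.

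The cost is a few lines in 3.3.2, 3.4.1, 3.4.2 and 3.5.1, plus one extra model per stratum, on variables the protocol already defines. The drawback is that the adjusted ratio may lie closer to 1 if the eosinophil effect is persistent. The report should say that it addresses a different question from the main model.
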